### **5.3. Medical History**

Medical history will be collected at screening including HIV-1 related disease events. Medical history data will be coded and listed.

## **6. EFFICACY ANALYSES**

### **6.1. Primary Efficacy Endpoint**

The primary efficacy endpoint is the proportion of participants in Cohort 1 achieving  $\geq 0.5 \log_{10}$  reduction from baseline in HIV-1 RNA at the end of the Functional Monotherapy Period.

The statistical analysis methods for the primary efficacy endpoint were described in the Week 26 SAP, and the analysis was performed in the Week 26 analysis.

### **6.2. Secondary Efficacy Endpoints**

The secondary efficacy endpoints are:

- The proportion of participants in Cohort 1 with plasma HIV-1 RNA  $< 50$  copies/mL and  $< 200$  copies/mL at Weeks 26 and 52 visits based on the United States (US) Food and Drug Administration (FDA)-defined snapshot algorithm.
- The proportion of participants in combined Cohorts 1 and 2 with plasma HIV-1 RNA  $< 50$  copies/mL and  $< 200$  copies/mL at Weeks 104 and 156 from the first SC dose of GS-6207 based on the US FDA-defined snapshot algorithm.

Analysis will be based on the FAS for All LEN Analysis. This SAP describes the statistical analysis methods for the proportion of participants in combined Cohorts 1 and 2 with plasma HIV-1 RNA  $< 50$  copies/mL and  $< 200$  copies/mL at Weeks 104 and 156 from the first SC dose of GS-6207 based on the US FDA-defined snapshot algorithm.

#### **6.2.1. US FDA-defined Snapshot Algorithm**

The analysis window at Week 104 is defined as from Study Day 688 to Study Day 778, inclusive, where Study Day is calculated from the first dose of oral LEN. Participants who have missing HIV-1 RNA at Week 104 and have completed the study before reaching the upper limit of the analysis window for Week 104 will be excluded. All HIV-1 RNA data collected on-treatment will be used in the snapshot algorithm.

HIV-1 RNA on-SC-LEN-treatment is defined as HIV-1 RNA collected up to 28 weeks from the last SC LEN, and on or prior to the first dose of oral bridging of LEN or up to 28 weeks from any resumed SC LEN after oral bridging for participants who received oral bridging of LEN.

HIV-1 RNA on-oral-LEN-treatment is defined as HIV-1 RNA collected after the First Dose Date of Oral Bridging or oral reload after the first SC LEN, and up to 7 days from the Last Dose Date of Oral Bridging for participants who discontinued from the oral bridging of LEN, or up to minimal (Last Dose Date of Oral Bridging +7, First Dose Date of Resumed SC Injection) for participants who resumed SC LEN.

For the snapshot algorithm, HIV-1 RNA on-SC-LEN-treatment will be used. If there is no such result, HIV-1 RNA on-oral-LEN-treatment will be used.

Virologic outcome will be defined as the following categories:

- HIV-1 RNA < 50 copies/mL: this includes participants who have the last available on-treatment HIV-1 RNA < 50 copies/mL in the Week 104 analysis window
- HIV-1 RNA  $\geq$  50 copies/mL: this includes participants
  - Who have the last available on-treatment HIV-1 RNA  $\geq$  50 copies/mL in the Week 104 analysis window, or
  - Who do not have on-treatment HIV-1 RNA data in the Week 104 analysis window and
    - Who discontinue study drug prior to or in the Week 104 analysis window due to lack of efficacy, or
    - Who discontinue study drug prior to or in the Week 104 analysis window due to reasons other than AE, death, or lack of efficacy and have the last available on-treatment HIV-1 RNA  $\geq$  50 copies/mL
- No Virologic Data in the Week 104 analysis window: this includes participants who do not have on-treatment HIV-1 RNA data in the Week 104 analysis window because of the following:
  - Discontinuation of study drug prior to or in the Week 104 analysis window due to AE or death (regardless of whether the last available on-treatment HIV-1 RNA < 50 copies/mL or not) or,
  - Discontinuation of study drug prior to or in the Week 104 analysis window due to reasons other than AE, death, or lack of efficacy and the last available on-treatment HIV-1 RNA < 50 copies/mL or,
  - Missing data during the window but on study drug.

The number and percentage of participants with HIV-1 RNA < 50 copies/mL, HIV-1 RNA  $\geq$  50 copies/mL, and reasons for no virologic data at Week 104 will be summarized. The 95% CI for the percentage of participants with HIV-1 RNA < 50 copies/mL will be constructed using the Exact method.

The proportion of participants with HIV-1 RNA < 200 copies/mL at Week 104, and the proportion of participants with HIV-1 RNA < 50 copies/mL and < 200 copies/mL at Week 156 will also be summarized in the same manner using the US FDA-defined snapshot algorithm. The analysis window at Week 104 is defined as from Study Day 779 to Study Day 869, inclusive.

The flowchart of the US FDA-defined snapshot algorithm is provided in Section 12 ([Appendix 1](#)).

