
Target Population:
	
Heavily treatment-experienced adults and adolescent PWH with resistance to ≥ 2 antiretroviral (ARV) medications from each of ≥ 3 of the 4 main classes of ARV medication and plasma HIV-1 RNA ≥ 400 copies/mL at screening while taking a failing regimen.
 
Adolescent participants will be enrolled only at sites in North America and Dominican Republic.

Duration of Treatment:
	
Duration of treatment is at least 54 weeks.
 
Following successful completion of Week 52 visit, participants will be given the option to attend visits at Week 62, 78, 88, 104, 114, 130 and will continue to alternate between every 10 weeks and every 16 weeks. Participants willing to continue the study beyond Week 52 will receive SC LEN 927 mg once every 6 months (26 weeks) ± 2 weeks from last injection starting at Week 52 visit, while continuing their OBR, until the product becomes accessible to participants through an access program, is commercially available, or until Gilead elects to discontinue the study in the country.
 
Participants who decide not to receive SC LEN at Week 52 and not to continue the study will complete the study at Week 52 visit.
 
At Week 156 and thereafter, upon regulatory and/or institutional review board (IRB)/independent ethics committee (IEC) approval of the protocol and when participants have provided written informed consent of the most current IRB-approved consent form, participants will continue to receive study drug every 26 weeks, and continue to attend visits every 26 weeks (± 2 weeks). Participants will receive SC LEN every 6 months (26 weeks) ± 2 weeks from the last injection starting at the Week 156 visit, while continuing their OBR, until the product becomes accessible to participants through an access program, is commercially available, or until Gilead elects to discontinue the study in the country.
 
Participants who decide to discontinue SC LEN early and do not wish to continue to attend study visits through the Week 156 visit or the next scheduled SC dosing visit will return to the clinic for 30-day, 90-day, and 180-day follow-up visits after the early termination visit. The 180-day follow-up may be conducted via a phone call per the investigator's discretion.

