If there are any abnormal laboratory results with a possible or probable causal relationship with the study drug, every attempt should be made to keep the participant in the study and repeat those laboratory tests weekly (or as often as deemed prudent by the investigator) until the abnormality is resolved, returns to baseline, or is otherwise explained. If this is not possible or acceptable to the participant or investigator, the participant may be withdrawn from the study.

If there are any AEs, every attempt should be made to keep the participant in the study and should be followed up until the AE is resolved or stable. Gilead may request that certain AEs be followed beyond the protocol-defined follow-up period. If this is not possible or acceptable to the participant or investigator, the participant may be withdrawn from the study.

The following evaluations should be performed at the early termination visit:

- Review of AEs and changes in concomitant medications.
- Symptom-directed physical examination (urogenital/anorectal examinations will be performed at the discretion of the investigator).
- Vital signs measurement (blood pressure, pulse, respiration rate, and temperature).
- Obtain blood and urine samples as noted in Section 6.5.
- Counsel participant regarding the importance of continuing a complete ART regimen in accordance to standard of care, and refer patient to an appropriate HIV treatment facility.

6.4.2. 30-Day, 90-Day, and 180-Day Follow-Up Visits

The assessments below will be completed for participants who are required to complete 30-day, 90-day, and/or 180-day follow-up visits as noted in Section 6.4.1. Follow-up visits will be scheduled based on the date of the early termination visit. No follow-up visits are required for those participants who do not receive SC LEN at the Week 52 visit.

For scheduling the follow-up visits, a \pm 6-day window may be used.

The following evaluations are to be completed at the follow-up visits:

- Review of AEs and changes in concomitant medications.
- Symptom-directed physical examination.
- Vital signs measurement (blood pressure, pulse, respiration rate, and temperature), including weight.
- Obtain blood and urine samples as noted in Section 6.5.

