8.2.3. Year 2 Analysis

The Year 2 Analysis will be performed after all participants in both cohorts have had HIV-1 RNA data in the Week 104 analysis window (or reached the upper limit of the analysis window with missing HIV-1 RNA data), or have prematurely discontinued the study drug, outstanding data queries have been resolved or adjudicated as unresolvable, and the data have been cleaned and finalized.

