In addition, the proportion of participants in Cohort 1 with HIV-1 RNA < 50 copies/mL and < 200 copies/mL at Week 52, and the proportion of participants in combined Cohorts 1 and 2 with HIV-1 RNA < 50 copies/mL and < 200 copies/mL at Weeks 104 and 156 (from the first SC dose of LEN) will also be summarized using the US FDA–defined snapshot algorithm. The analysis window at Week 52 is defined as from Study Day 324 to Study Day 414, inclusive. The analysis window at Week 104 is defined as from Study Day 688 to Study Day 778, inclusive. The analysis window at Week 156 is defined as from Study Day 1052 to Study Day 1142, inclusive. The secondary endpoints will be based on the FAS for the All LEN analysis. Analysis will be based on participants who receive at least 1 dose of SC LEN.

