### **2.1.5. Year 2 Analysis**

The Year 2 Analysis will be performed after all participants in both cohorts have had HIV-1 RNA data in the Week 104 analysis window (or reached the upper limit of the analysis window with missing HIV-1 RNA data), or have prematurely discontinued or completed the study drug, outstanding data queries have been resolved or adjudicated as unresolvable, and the data have been cleaned and finalized.

This SAP describes the analysis plan for the Year 2 Analysis.

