#### **6.3.2. Analysis of Other Efficacy Endpoints**

Baseline and the change from baseline in HIV-1 RNA ( $\log_{10}$  copies/mL) and CD4 cell count (/uL) by visit for All LEN Analysis will be summarized using descriptive statistics.

Mean  $\pm$  95% CI of the change from baseline in HIV-1 RNA ( $\log_{10}$  copies/mL) will be plotted by visit.

Number and percentage of participants with HIV-1 RNA < 50 copies/mL by visit will be analyzed using the following analyses:

- Missing = Failure (M = F):

In this approach, missing data will be treated as virologic failure and summarized into the “missing” category (see list of HIV-RNA categories below). The denominator for percentages at a visit is the number of participants in the FAS, excluding ongoing participants who have missing HIV-1 RNA at a visit and have not reached the upper limit of the analysis window for the corresponding visit and participants who have missing HIV-1 RNA at a visit and have completed the study before reaching the upper limit of the analysis window for the corresponding visit.

- Missing = Excluded (M = E):

In this approach, missing data will be excluded in the computation of the percentages (ie, missing data points will be excluded from both the numerator and denominator in the computation). The denominator for percentages at a visit is the number of participants in the FAS with nonmissing HIV-1 RNA value at that visit.

No statistical testing is planned. The number and percentage of participants with HIV-1 RNA in the following categories will be summarized:

- < 50 copies/mL
  - < 20 copies/mL
    - < 20 copies/mL Not Detectable
    - < 20 copies/mL Detectable
  - 20 to < 50 copies/mL
- 50 to < 200 copies/mL
- 200 to < 400 copies/mL
- 400 to < 1000 copies/mL
- $\geq$  1000 copies/mL
- Missing (only applicable to M = F analysis)

Analysis of the other efficacy endpoints will be based on the FAS.

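### Early completers with missing HIV-1 RNA are dropped from the Week 104 and 156 snapshot and from Missing = Failure; the change is not declared and no full-denominator result is planned

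*SAP*

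**What the plan says.** **Snapshot.** At Week 104, SAP 6.2.1 excludes "Participants who have missing HIV-1 RNA at Week 104 and have completed the study before reaching the upper limit of the analysis window". It then says that the 200 copies/mL threshold and the Week 156 results are summarized in the same way, which carries the rule to Week 156 by reference.

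**By-visit analyses.** In SAP 6.3.2 the Missing = Failure denominator leaves out "participants who have missing HIV-1 RNA at a visit and have completed the study before reaching the upper limit of the analysis window", as well as ongoing participants who have not yet reached the end of the window. Missing = Excluded drops every missing value by design.

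**Protocol.** Section 8.5.2 places the Week 104 and 156 endpoints on the FAS for the All LEN analysis and adds one restriction: "Analysis will be based on participants who receive at least 1 dose of SC LEN". Its snapshot categories cover data in the window, discontinuation of study drug, and missing data while on study drug. They do not say where a study completer belongs.

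**Analysis trigger.** Protocol 8.2.3 lets the Year 2 analysis start once participants have window data, have passed the window, "or have prematurely discontinued the study drug". SAP 2.1.5 widens the last condition to those who "have prematurely discontinued or completed the study drug".

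**Declared changes.** SAP 6.5 states that there are none for efficacy.

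**Who is a completer.** In the protocol synopsis (Duration of Treatment), participants who decline SC LEN at Week 52 and decide "not to continue the study will complete the study at Week 52 visit". No viral-load condition is attached. Protocol 6.4.2 adds: "No follow-up visits are required for those participants who do not receive SC LEN at the Week 52 visit".

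**The concern.** In this protocol completion is not purely administrative. It includes a participant's own choice to stop at Week 52, and a viremic participant can make that choice. If that person is recorded as a completer, the SAP removes them from the snapshot and from Missing = Failure, and Missing = Excluded never contained them. Missing = Failure would normally expose such losses, but here it cannot, because it carries the same exclusion.

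The Week 104 and 156 endpoints were added in Amendment 4 to support durability of response, so who leaves the denominator bears directly on the claim. The planned disposition tables count completers but give reasons only for premature discontinuation. Nothing sets the excluded completers' last HIV-1 RNA or reason for completing beside the result, so a reader cannot tell suppressed participants who moved to accessible product from viremic participants who opted out.

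**Working it through.** **The plan's own figure.** The documents give no rate, precision or expected number excluded for Weeks 104 and 156, so there is nothing to reproduce for these endpoints. The only design figure is the Cohort 1 power of at least 90%. Exact enumeration of the Fisher test (24 against 12, 70% against 10%, 2-sided 0.05) gives 95.1%, which agrees with it, but this point does not depend on it.

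**Step 1: two comparable participants under the SAP's own rules.** Inputs are the nominal days in SAP Table 3-1 (Week 26 = Day 197, Week 52 = Day 379), the opening of the Week 104 window at Day 688, and the SAP 6.2.1 on-treatment rule, "HIV-1 RNA collected up to 28 weeks from the last SC LEN" (28 × 7 = 196 days). No oral bridging is assumed.

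| | Declines the Week 52 injection and leaves | Takes the Week 52 injection, then stops |
|---|---|---|
| Last injection | Day 197 | Day 379 |
| On-treatment RNA ends | 197 + 196 = Day 393 | 379 + 196 = Day 575 |
| Gap to the Week 104 window | 688 − 393 = 295 days | 688 − 575 = 113 days |
| Status | Study completer | Premature discontinuation |
| If last RNA ≥ 50 and the reason is not AE or death | Excluded | Counted as ≥ 50 copies/mL |

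Neither has on-treatment data in the window. The completion label alone decides whether a viremic participant counts as a failure or disappears.

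**Step 2: direction.** Let x be the successes, N the full denominator and k the excluded completers. The SAP reports x/(N − k), against x/N for the full denominator. The ratio is N/(N − k), which is at least 1. An excluded person has no window RNA and so cannot be in x. The rule can therefore only leave the rate unchanged or raise it.

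**Step 3: illustrative size.** N should be the SC-dosed set, which is not given. The 72 enrolled (Protocol 1.2.2.2) is used as a stand-in, and x = 50 is assumed. Intervals are exact 95%.

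| k | SAP rule | Full denominator | If all k were in fact suppressed |
|---|---|---|---|
| 0 | 50/72 = 69.4% (57.5–79.8) | 69.4% | 69.4% |
| 3 | 50/69 = 72.5% (60.4–82.5) | 69.4% | 53/72 = 73.6% |
| 5 | 50/67 = 74.6% (62.5–84.5) | 69.4% | 55/72 = 76.4% |
| 10 | 50/62 = 80.6% (68.6–89.6) | 69.4% | 60/72 = 83.3% (72.7–91.1) |

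Sensitivity to N at k = 10: for N = 70, 50/60 = 83.3% against 50/70 = 71.4%; for N = 68, 50/58 = 86.2% against 50/68 = 73.5%. If instead about 80% of those kept respond (N = 72), the gap is 3.3 points at k = 3 (55/69 against 55/72) and 7.8 points at k = 7 (52/65 against 52/72).

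**Step 4: what is known about k.** The Amendment 5 log in Protocol Appendix 7 says 13 participants remained, so 72 − 13 = 59 had left. The documents do not split these by completion or discontinuation, or by before or after a window, so this does not fix k.

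**The case against.** The strongest reply is that the SAP fills a gap and contradicts nothing. The protocol's snapshot has no place for a study completer, and people who leave because the product has become accessible or marketed are administrative losses, for whom exclusion is a reasonable choice. That stands as a defence of the choice. It does not make the choice invisible: the rule alters the denominator of a secondary endpoint and should be declared.

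Other points also stand in part:

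- The protocol plans no Missing = Failure analysis, so only the snapshot rule is an addition to a protocol-specified analysis. For Missing = Failure, the issue is that it does not supply the full denominator its name suggests. The trigger wording concerns timing and is secondary.
- k may be 0, and completers may be suppressed. The last column of the table shows that the SAP rate can lie below the truth.
- Completion at Week 52 is set out in the synopsis, whereas Protocol 3.4 describes completion on declining only at Week 156. Protocol 6.4.2 supports the Week 52 reading.
- Completer counts in the disposition tables and the reduced snapshot denominator let a reader infer that people are missing, but not their reason or last HIV-1 RNA.
- The SAP is based on Amendment 4, and the protocol available is Amendment 5. The Amendment 5 log lists no change to Section 8, so the comparison is fair.
- The endpoints are descriptive, and the primary, Week 26 and Week 52 analyses are already done. Alpha and power are untouched. For a descriptive endpoint, however, the percentage and its interval are the result, and the denominator determines both.

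**Conclusion.** The concern holds and should be fixed. The exclusion is explicit for Week 104 and for Missing = Failure, and applies to Week 156 by reference. It is undeclared, and no planned analysis restores the full denominator. Relative to a full-denominator snapshot its direction is certain: unchanged or higher, by the factor N/(N − k). Its size is unknown. The illustration of 3.1 points at k = 3 (72.5 − 69.4) and 11.2 points at k = 10 (80.6 − 69.4) rests on assumed values of N, k and the number of successes.

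Inflation over true suppression is not established. What is established is that viremic and suppressed completers are treated alike by removal, while a viremic participant who stops after the Week 52 injection can count as a failure, and that the planned output does not let a reader judge which kind of completer was removed.

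**What to change.** 1. Declare the completer exclusion in SAP 6.5, with its reason, and say explicitly that it applies at Week 156.
2. For Weeks 104 and 156, report the number of excluded completers, their reason for completion and their last on-treatment HIV-1 RNA.
3. Keep the planned result and show beside it a full-denominator snapshot and a full-denominator Missing = Failure. Use the FAS with at least one SC LEN dose, as in Protocol 8.5.2. SAP 6.2 names the FAS without that restriction, so state which set applies.
4. In the full-denominator snapshot, count early completers whose last on-treatment HIV-1 RNA was ≥ 50 copies/mL in the ≥ 50 category. Show those below 50 in a separate no-virologic-data row for completion before the window. Apply the same rule at 200 copies/mL.

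The cost is one line in SAP 6.5 and one or two tables from data already held. The full-denominator percentage may be less favourable and may understate suppression among purely administrative completers, which is why both versions should appear together.

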6.4. Posttreatment Assessments

6.4.1. Early Termination Visit Assessments

6.4.1.1. Early Termination Visit After Day 1 and Prior to Day 1 SC

If a participant discontinues oral LEN or decides not to initiate SC LEN at Day 1 SC, an early termination visit should be performed within 72 hours of decision to discontinue the study drug. Participants in Cohort 1 will be asked to continue to attend study visits until completion of the Functional Monotherapy Period. Participant will be required to complete the 90-day follow-up visit. Refer to Section 6.4.2.

6.4.1.2. Early Termination Visit After Day 1 SC and Prior to Week 52

If a participant decides to discontinue SC LEN prior to Week 52, an early termination visit should be performed within 72 hours of decision to discontinue study drug.

The participant will be asked to continue attending the scheduled study visits through the Week 52 visit.

- If the participant decides to discontinue SC LEN and agrees to continue to attend study visits through Week 52, no follow-up visits are required.
- If the participant decides to discontinue SC LEN and does not agree to continue to attend study visits through Week 52, the 30-day, 90-day, and 180-day follow-up visits are required. Refer to Section 6.4.2. The 180-day follow-up may be conducted via a phone call per the investigator's discretion.

6.4.1.3. Early Termination Visit After Week 52

If a participant continues the study after completing the Week 52 visit, but discontinues SC LEN prior to study completion, an early termination visit should be performed.

- If the participant discontinues LEN (SC and oral) and continues to attend study visits through their next SC dosing visit, all assessments, except SC dosing, will be performed at the last visit. No further follow-up visits are required.
- If the participant discontinues SC LEN and does not continue to attend study visits through the participant's next SC dosing visit, the 30-day, 90-day, and 180-day follow-up visits are required. Refer to Section 6.4.2. The 180-day follow-up may be conducted via a phone call per the investigator's discretion.
- If a participant discontinues oral LEN during the Oral Bridging Period and does not continue to attend study visits through their next SC dosing visit, the participant will be required to complete the 90-day follow-up visit (see Section 6.4.2).

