If there are any abnormal laboratory results with a possible or probable causal relationship with the study drug, every attempt should be made to keep the participant in the study and repeat those laboratory tests weekly (or as often as deemed prudent by the investigator) until the abnormality is resolved, returns to baseline, or is otherwise explained. If this is not possible or acceptable to the participant or investigator, the participant may be withdrawn from the study.

If there are any AEs, every attempt should be made to keep the participant in the study and should be followed up until the AE is resolved or stable. Gilead may request that certain AEs be followed beyond the protocol-defined follow-up period. If this is not possible or acceptable to the participant or investigator, the participant may be withdrawn from the study.

The following evaluations should be performed at the early termination visit:

- Review of AEs and changes in concomitant medications.
- Complete physical examination (urogenital/anorectal examinations will be performed at the discretion of the investigator).
- Vital signs measurement (blood pressure, pulse, respiration rate, and temperature).
- Weight.
- Obtain blood and urine samples as noted in Section 6.5.
- Counsel participant regarding the importance of continuing a complete ART regimen in accordance to standard of care, and refer patient to an appropriate HIV treatment facility.

6.4.1.4. Early Termination Visit After Week 156

If a participant continues the study after completing the Week 156 visit, but discontinues SC LEN prior to study completion, an early termination visit should be performed.

- If the participant discontinues LEN (SC) and continues to attend study visits through their next SC dosing visit, all assessments, except SC dosing, will be performed at the last visit. No further follow-up visits are required.
- If the participant discontinues SC LEN and does not continue to attend study visits through the participant's next SC dosing visit, the 30-day, 90-day, and 180-day follow-up visits are required. Refer to Section 6.4.2. The 180-day follow-up may be conducted via a phone call per the investigator's discretion.

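### The SAP's on-treatment rule does not end when replacement antiretrovirals are started after LEN is stopped, so suppression on new drugs can count as Week 104 or Week 156 success

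*SAP*

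**What the plan says.** SAP 6.2.1 defines the values that feed the snapshot: "HIV-1 RNA on-SC-LEN-treatment is defined as HIV-1 RNA collected up to 28 weeks from the last SC LEN". For participants who bridge orally, those values must also be "on or prior to the first dose of oral bridging of LEN", or fall within 28 weeks of a resumed injection. No other event closes the interval.

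The classification then runs in a fixed order. If the window contains an on-treatment value, the last one decides the outcome. Only participants without such a value go to the branches that use the reason for discontinuation, including the one that makes lack of efficacy a failure: "Who discontinue study drug prior to or in the Week 104 analysis window due to lack of efficacy, or". Protocol 8.5.2 gives the same order and uses the term on-treatment without defining it. SAP Appendix 2 refers back to 6.2.1 for the definition.

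HIV-1 RNA continues to be drawn after LEN is stopped. Under Protocol 6.4.1.3, a participant who stops after Week 52 and "continues to attend study visits through their next SC dosing visit, all assessments, except SC dosing, will be performed at the last visit". Otherwise there are 30-, 90- and 180-day follow-up visits. Protocol Appendix 2 schedules plasma HIV-1 RNA at early termination and at follow-up. The early termination visit also includes this instruction: "Counsel participant regarding the importance of continuing a complete ART regimen in accordance to standard of care".

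Protocol 5.5 allows OBR changes for efficacy, safety or tolerability. SAP 7.4.1.3 lists participants with such changes but attaches no outcome rule. SAP 6.5 declares no change from the protocol's efficacy analysis.

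**The concern.** The secondary objective concerns LEN together with an OBR at Weeks 104 and 156. Once LEN has been stopped and other antiretrovirals have replaced or joined the background, a value below 50 copies/mL no longer measures that strategy alone, even though some LEN is still present. Under the SAP, one such value inside the window overrides a recorded discontinuation for lack of efficacy, which would otherwise be a failure. It equally overrides a discontinuation for an adverse event, which would otherwise be no virologic data.

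The endpoint pools both cohorts without a control arm, so nothing offsets an error in one direction. The error will mostly be upward. Removing values drawn after new drugs were started can raise the proportion only if an earlier in-window value was below 50 and a later one was not.

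**Working it through.** **Inputs.**
- On-treatment limit: 28 weeks = 196 days after the last injection (SAP 6.2.1).
- Week 104 window: "The analysis window at Week 104 is defined as from Study Day 688 to Study Day 778, inclusive" (SAP 6.2.1).
- Week 156 window: "The analysis window at Week 156 is defined as from Study Day 1052 to Study Day 1142, inclusive" (Protocol 8.5.2; SAP Table 3-1 agrees). The end of SAP 6.2.1 prints Days 779 to 869, again labelled Week 104, where the Week 156 window is expected. Table 3-1 gives those days to Week 114, so they are not used here.
- Injection interval: 26 weeks = 182 days (SAP 4.2).
- Enrolment: 72 (Protocol 1.2.2.2).

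**Reproducing the plan's nominal days.** Day 1 SC is Study Day 15, so nominal day = 15 + 7 × week. Week 104: 15 + 728 = 743. Week 156: 15 + 1092 = 1107. Both match Table 3-1.

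**Overlap of the 28 weeks with each window.** Each window has 91 days (778 − 688 + 1; 1142 − 1052 + 1).

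| Last injection | Day | On-treatment to | Window days covered | Nominal visit covered? |
|---|---|---|---|---|
| Week 78 | 561 | 561 + 196 = 757 | 757 − 688 + 1 = 70 | Yes (743) |
| Week 130 | 925 | 925 + 196 = 1121 | 1121 − 1052 + 1 = 70 | Yes (1107) |

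Moving the injection two weeks earlier or later changes coverage to 56 or 84 days, and the nominal visit stays inside in every case.

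**Who cannot be affected.** A participant last injected at Week 52 (Day 379) is covered only to Day 575, before the Week 104 window opens. One last injected at Week 104 (Day 743) is covered only to Day 939, before the Week 156 window opens. In general the last injection must fall on or after Day 492 (688 − 196) for Week 104, or Day 856 (1052 − 196) for Week 156.

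**Worked case.** Last injection on Day 561; LEN stopped for lack of efficacy at Week 88 (Day 631) and new antiretrovirals started. The 90-day follow-up falls on 631 + 90 = Day 721, or Days 715 to 727 with the ±6-day allowance in Protocol 6.4.2. That is inside the window and before Day 757, so a value below 50 is a Week 104 success. With no in-window value, the same participant is counted as 50 or above. Any early termination visit on Days 598 to 667 puts its nominal 90-day visit in the covered stretch (688 − 90; 757 − 90).

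**Size.** One participant is 1/72 = 1.4 points, two are 2.8 and four are 5.6. As an illustration only, take an assumed 58/72 = 80.6% (exact 95% CI 69.5 to 88.9). Reclassifying one, two or four gives 79.2% (68.0 to 87.8), 77.8% (66.4 to 86.7) or 75.0% (63.4 to 84.5). Both the base rate and the counts are assumptions.

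**The case against.** The strongest defence is pharmacological. Twenty-eight weeks is the dosing interval plus its two-week allowance, and LEN is long-acting, so a participant who has decided to stop is still exposed. That stands: 28 weeks is a reasonable outer limit, and a reader who infers that the limit itself is wrong goes too far. What it does not answer is the missing rule for replacement drugs.

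Other points narrow the finding:
- A reader might infer that every value within 28 weeks counts. It does not, because oral bridging ends the interval.
- A reader might infer that the protocol makes suppression on new drugs likely. It makes sampling after stopping likely. Eligibility allowed at most two fully active agents from the four main classes, the background was already optimized, and participants with lack of efficacy may stay on LEN (Protocol 6.6). The counselling text speaks of continuing treatment and does not show that new drugs are started.
- The branch order follows Protocol 8.5.2. The gap is in the on-treatment definition, which the protocol leaves open.
- The rule is symmetric in form, since a rebound within 28 weeks counts against LEN. Effective new drugs nevertheless push values in one direction.
- The by-visit missing = failure and missing = excluded analyses also set no on-treatment limit. A reader might call that a fault, but they are supportive endpoints, and using all observed values is a legitimate choice. The sentence "The denominator for percentages at a visit is the number of participants in the FAS with nonmissing HIV-1 RNA value at that visit" only fixes a denominator.
- Listings of OBR changes, antiretrovirals and discontinuation reasons would let a reader find the cases. They do not change the reported proportion.

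**Conclusion.** The gap is real and limited. As written, the snapshot can count suppression on newly started antiretrovirals after LEN discontinuation as a Week 104 or Week 156 success, for participants whose last injection was around Week 78 or Week 130. Coverage of 70 of 91 days and of the nominal visit follows from the plan's own numbers.

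The shift of about 1.4 points per participant assumes N = 72. The actual denominator may be smaller, because Protocol 8.5.2 refers to participants who received SC LEN and SAP 6.2.1 excludes some study completers with missing values; each case would then weigh slightly more. The number of cases is not in the documents, so they do not support a claim that the reported proportions are materially inflated.

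The endpoints are secondary and descriptive, and the primary endpoint is untouched. The point is still worth correcting before results are seen: SAP section 1 says the SAP is finalized before Year 2 data finalization.

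**What to change.** In SAP 6.2.1, keep 28 weeks as the outer limit. For participants who discontinue study drug, end on-treatment HIV-1 RNA at the earlier of:
1. 28 weeks after the last SC LEN injection; and
2. the day before the first antiretroviral that is not in the current OBR and was started after that injection (ARV eCRF).

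Then classify them with the existing discontinuation-reason branches. Anchoring on the injection rather than on the decision to stop also catches drugs started shortly before that decision, and needs no decision date, which SAP 3.8.1 does not define. The SAP should say what current OBR means here, for example the background drugs in use on the day of the last injection. Apply the rule at Weeks 104 and 156 for both the 50 and the 200 copies/mL thresholds, and list it in SAP 6.5.

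If the sponsor prefers to leave the main rule consistent with earlier time points, the minimum is a prespecified sensitivity analysis with this cut-off. It should also not count as success any value obtained after an OBR change made for efficacy while LEN continues, because the main fix does not reach those participants. No change to the missing = failure or missing = excluded analyses is needed.

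The cost is SAP wording and one derived date. SAP 7.4.1 says antiretrovirals after the study are recorded if collected, so completeness of start dates after discontinuation should be checked. The reported success proportion may be slightly lower.
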